2.3.3 Overall Benefit: Risk Conclusion

Considering the measures taken to minimize risk to participants in this study, the potential risks identified are justified by the anticipated benefits that may be afforded to patients with cIAI.

3 OBJECTIVES

Table 1 Study Objectives and Endpoints

Objectives	Endpoints
Primary	
Characterize the PK of metronidazole and its metabolite 2-hydroxymetronidazole in the plasma and intestinal wall of healthy infants undergoing intestinal surgeries	Primary and secondary PK parameters including clearance, half-life, volume of distribution, and AUC
Secondary	
Characterize the contribution of intestinal CYP2A6 to the metabolism of metronidazole	CYP2A6 quantification, ratios of metronidazole to 2-hydroxymetronidazole concentrations, ratios of metronidazole in plasma/intestine, ratios of 2-hydroxymetronidazole concentration in plasma/intestine

3.1 Study Outcome Measures

3.1.1 Primary Outcome Measures

- 1) PK parameters after administration of metronidazole and its metabolite 2-hydroxymetronidazole in the plasma and intestinal wall which may include:
 - Clearance (CL)
 - Half-life (t_{1/2})
 - Volume of distribution (V)
 - Area under the curve (AUC)

3.1.2 Secondary Outcome Measures

- 1) CYP2A6 quantification and other metabolizing and transporter enzymes
- 2) Ratios of metronidazole to 2-hydroxymetronidazole concentrations
- 3) Ratios of metronidazole in plasma/intestine
- 4) Ratios of 2-hydroxymetronidazole concentration in plasma/intestine

4 Study Design

Single center, open-label, non-randomized study to assess the intestinal pharmacokinetic profile of metronidazole in healthy children \leq 2 years of age undergoing elective intestinal operations for non-infectious conditions.

4.1 Number of Desired Participants:

A 20 infant sample size is derived to meet the primary objective of characterizing the PK of metronidazole in plasma and the intestinal wall of infants. Two desired gestational age ranges will be included in this study:

- < 34 weeks gestational age
- ≥ 34 weeks gestational age

[figure not shown]
All efforts will be made to approximately stratify enrollment as outlined in table 2.

Table 2 Age Stratification

Age	N = 20
< 34 weeks gestational age at birth	10
≥ 34 weeks gestational age at birth	10

Note: "Enrolled" means a participant's, or their legally acceptable representative's, agreement to participate in a clinical study after completion of the informed consent process. Potential participants who are screened for the purpose of determining eligibility for the study, but do not participate in the study, are not considered enrolled, unless otherwise specified by the protocol.

4.2 Study Schema

5 Study Population

5.1 Inclusion Criteria

1. Age 0 to \leq 2 years
2. Written informed consent provided by a parent or legal guardian
3. Scheduled to undergo elective intestinal operation for the removal of non-infected, otherwise healthy bowel
4. Sufficient intravascular access to complete the study procedures

5.2 Exclusion Criteria

- 1) Prior treatment with metronidazole for any dose during the 72 hours prior to study drug administration.
- 2) Patients with active inflammatory or infectious conditions of the bowel such as inflammatory bowel disease, Hirschprung's disease in the portion of bowel to be excised, diverticular disease, cancerous or pre-cancerous lesions, colitis, enteritis, ulcerative disease, Meckel's diverticulum, celiac disease, and irritable bowel syndrome.
- 3) Renal dysfunction defined as serum creatinine >2 mg/d at any time during the preoperative period.
- 4) Receiving any extracorporeal life support including extracorporeal membrane oxygenation, ventricular assist devices, and renal replacement therapy.
- 5) Any condition or circumstance that, in the opinion of the investigator, would compromise the safety of the participant or the quality of the data.

5.3 Duration of Study Participation

The maximum duration of participation is approximately 60 days: Screening Period of approximately 30 days, a 1-day Treatment Period on the day of the operation, and a 30-day Follow-Up Period.

5.3.1 Replacement Participants

Because accurate characterization of PK in a small sample size of patients is dependent upon adequate sampling, participants in this study who are unable to provide at least 1 timed PK sample may be replaced. The replaced patient will be considered an early withdrawal from the study and will be monitored for AEs related to study procedures, complications, and events of special interest as per protocol. The data collected from the replaced patient will be retained and included in the study results.

5.3.2 Reasons for Participant Withdrawal

A participant's parent/guardian may voluntarily discontinue their child's participation in this study at any time. The investigator may also, at his/her discretion; withdraw the participant from this study at any time. Participants may be prematurely discontinued from the study for any of the following reasons:

- Participant or investigator noncompliance with the study protocol
- At the request of the participant's parent/guardian, investigator, or sponsor
- Safety concerns

Participants are not obligated to state the reason for withdrawal. The reasons for withdrawal, or failure to provide a reason, must be documented by the investigator on the completion/ withdrawal section of the CRF. Any participant who withdraws early or is withdrawn early will be requested to complete end-of-study safety evaluations and will be provided appropriate care under medical supervision until the symptoms of any events of special interest resolve or the participant's condition becomes stable. Participants withdrawn from the study due to an event of special interest must be followed per protocol (See Section 8)

5.3.3 Termination of Study

The study will be terminated upon study completion. The study is considered closed when all required documents and study supplies have been collected and a study-site closure meeting has occurred. The Investigator may initiate study closure at any time, provided there is reasonable cause and sufficient notice is given in advance of the intended termination.

Reasons for the early termination of the study may include but are not limited to:

- Failure of the investigator to comply with the protocol, the requirements of the IRB/IEC or local health authorities, the sponsor's procedures, or GCP guidelines
- Inadequate recruitment of participants by the investigator
- Discontinuation of further study intervention development

If the study is prematurely terminated or suspended, the investigators will notify, the IECs/IRBs, the regulatory authorities, and any contract research organization(s) used in the study of the reason for termination or suspension, as specified by the applicable regulatory requirements. The investigator shall promptly inform the participants and should assure appropriate therapy and/or follow-up as necessary.

6 STUDY PROCEDURES

6.1 Screening

Study procedures and their timing are summarized in the SoA. Protocol waivers or exemptions are not allowed unless approved by the study PI and IRB. Immediate safety concerns should be discussed with the PI immediately upon occurrence or awareness to determine if the participant should continue or discontinue study intervention. Adherence to the study design requirements, including those specified in the SoA, is essential and required for study conduct.

All screening evaluations must be completed and reviewed to confirm that potential participants meet all eligibility criteria. The investigator will maintain a screening log of consented patients to record details of all participants screened and to confirm eligibility or record reasons for screen failure, as applicable. Procedures conducted as part of the participant's routine preoperative management (eg, blood count, creatinine) and obtained before signing of the ICF may be used for screening or baseline purposes provided the procedures meet the protocol-specified criteria and are performed within the time frame defined in the SoA. If a patient does not have desired laboratory values, they will be obtained through standard of care measurements as able, most often occurring during preoperative visits to either surgery or anesthesia, in hospital consultations to surgery, or in the standard of care preoperative laboratory collection on the day of surgery.

This study will consist of a Screening, Treatment, and Postoperative Period.

6.2 Enrollment/Baseline

Screening Period (Day -30 to 0)

After the parent or legal guardian has signed the IRB-approved informed consent form/HIPAA authorization documents, and after it has been determined that the participant satisfies all inclusion and no exclusion criteria, the following evaluations will be extracted from the electronic medical record:

- 1) Participant demographics including gender, date of birth, postnatal age, race, gestational age at birth and birth weight
- 2) Physical examination and vital signs, including weight, height, heart rate, respiratory rate, oxygen saturation, and blood pressure, performed at any preoperative visit
- 3) Pertinent medical history, including diagnosis for which subject is undergoing surgery and history of genetic syndrome (i.e., trisomy 21)
- 4) The most recent laboratory determination in pre-operative visits, including serum creatinine, no blood draws will be performed just for the purposes of this study (See Section 6.6)
- 5) Adverse events related to study procedures

6.3 Treatment Procedures

Operative Day (Day 1)

The following assessments will be conducted on the day the patient is administered the study drug and undergoes surgery.

- 1) Date, time, dose, route, and duration of metronidazole administration
- 2) Physical examination and vital signs, including weight, height, heart rate, respiratory rate, oxygen saturation and blood pressure, can be performed prior to intubation on the day of surgery
- 3) Laboratory determinations, if available, no blood draws will be performed just for the purposes of this study (See Section 6.6)
- 4) Concomitant medications of interest
- 5) Collection of PK plasma and intestine samples (including date/time; See Section 6.6.2)
- 6) Results for laboratory tests of interests (See Section 6.6.1)
- 7) Events of special interest (See Section 8.1)
- 8) Adverse events related to study procedures (See Section 8.4)
- 9) Information regarding the surgery performed including: type of surgery, laparoscopic vs. open procedure; times of incision, intestinal excision, closure; intubation, extubation; estimated blood loss, blood transfusions given, amount and type of intravenous fluids given
- 10) Intraoperative complications including: unexpected alteration in operative plan, excessive blood loss, need for transfusion, damage to any structure, conversion from laparoscopic to open procedure, death (See Section 8.2)

6.4 Postoperative Period

The postoperative period of 30 days will be followed remotely through review of the electronic medical record. If no clinical contact has been made by the end of the postoperative period, study personnel will phone the parent/guardian to examine for any adverse events or hospitalizations to the participant.

- 1) Information regarding any adverse events related to metronidazole administration and/or study procedures (see section 8.4)
- 2) Information regarding events of special interest (See Section 8.1)
- 3) Information regarding postoperative complications including: any unexpected medical or surgical intervention, readmission for any reason, postoperative blood loss, transfusion requirements, infectious complications of any organ system or the wound, death (See section 8.3)

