Objectives:	
Primary:
 
 1) Characterize the PK of metronidazole and its metabolite 2-hydroxymetronidazole in the plasma and intestinal wall of healthy infants undergoing intestinal surgeries 
Secondary:
 
 1) Characterize the contribution of intestinal CYP2A6 metabolism on metronidazole
Study Design:	Prospective, single center, open-label, PK study
Study Population:	Children \leq 2 years of age undergoing intestinal surgery
Number of Participants:	Up to 20
Number of Sites:	1
Duration of Participant Participation:	Day of surgery. Remote monitoring of patient record for 30 days postoperatively
Dose Schedule:	Per routine medical care
Estimated Start:	May 2020
Estimated Time to Complete Enrollment:	18 months
Inclusion Criteria	
 1) Age 0 to \leq 2 years at enrollment 2) Written informed consent provided by a parent or legal guardian 3) Scheduled to undergo elective intestinal operation for the removal of non-infected bowel 4) Sufficient intravascular access to complete the study procedures
Exclusion Criteria:	
 1) Prior treatment with metronidazole for any dose during the 72 hours prior to study drug administration. 2) Patients with active inflammatory or infectious conditions of the bowel such as inflammatory bowel disease, Hirschprung's disease in the portion of bowel to be excised, diverticular disease, cancerous or pre-cancerous lesions, colitis, enteritis, ulcerative disease, Meckel's diverticulum, celiac disease, and irritable bowel syndrome. 3) Renal dysfunction defined as serum creatinine >2 mg/dL at enrollment

	
4) Receiving any extracorporeal life support including extracorporeal membrane oxygenation, ventricular assist devices, and renal replacement therapy at enrollment5) Any condition or circumstance that, in the opinion of the investigator, would compromise the safety of the participant or the quality of the data.
--	---

Table 1. Schedule of Study Procedures

Assessments	Screening Period Day -30 to 0	Treatment Period Operative Day, Day 1	Postoperative Period Day 2 to Day 31
Informed consent/assent	X		
Demographics ^a	X		
Clinical data ^b			
Medical history	X		
Physical examination	X	X	
Height/length and body weight	X	X	
Vital signs ^c	X	X	
Clinical laboratory parameters ^d	X	X	
Serum creatinine	X	X	
Study drug administration		X	
Events of Special Interest ^e		X	X

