8.3 Postoperative Complications

A postoperative complication will be limited to any issue arising after the patient leaves the operating room to 30 days after the operation. Postoperative complications are defined as any issue arising that

leads to alteration in the standard recovery pathway. All postoperative complications documented by the anesthesia or surgical teams in the electronic medical record will be collected and their severity will be classified using the Clavien-Dindo scale below¹⁵.

Clavien-Dindo Grade	Definition
Grade 0	Standard postoperative care without deviations from protocols
Grade 1	Any deviation from postoperative care without the need for pharmacologic, surgical, radiologic, or endoscopic interventions. (Allowed interventions – antiemetics, antipyretics, analgesics, diuretics, electrolytes, local wound care, and physiotherapy)
Grade 2	Requires pharmacologic treatment with drugs other than listed in grade 1, blood transfusions, or total parenteral nutrition
Grade 3	Requires surgical, endoscopic, or radiological intervention
Grade 4	Life-threatening complication with/ without intensive care unit management
Grade 5	Death

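### One early clinical contact cancels the only planned call to the parent, so the rest of the 30-day safety window rests on record review alone

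*Combined protocol and SAP*

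**What the plan says.** Section 6.4 sets up two layers of follow-up.

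- The first is passive and covers the whole window: "The postoperative period of 30 days will be followed remotely through review of the electronic medical record". The synopsis ("Remote monitoring of patient record for 30 days postoperatively") and Section 5.3 ("a 30-day Follow-Up Period") give the same length. Section 8.5 names the electronic health record as the monitoring source for all safety events, and Section 9 adds a search of that record for postoperative cultures.
- The second is active and conditional: "If no clinical contact has been made by the end of the postoperative period, study personnel will phone the parent/guardian", with the stated purpose "to examine for any adverse events or hospitalizations to the participant". The section does not define clinical contact, say when it must occur, or say what must be asked at it.

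The events to be collected in Section 6.4 include "readmission for any reason", infections of any organ system or the wound, and death. Section 8.3 opens the complication window early: "any issue arising after the patient leaves the operating room to 30 days after the operation". It also limits the source of postoperative complications to what the anesthesia or surgical teams have documented in the record. Section 10.2 says that adverse events and events of special interest will be summarized by age cohort. It gives no rule for incomplete follow-up and asks for no date of last known status.

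**The concern.** The call is there to find events that the record might not show. Its trigger, however, depends on whether any contact took place, not on whether the infant's status is known at the end of the window. An infant seen once in the first week and never again has nearly the same blind spot as an infant who was never seen, yet only the second family is phoned.

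At stake is how completely 30-day complications, readmissions and events of special interest are ascertained. Section 2.3.2 names pediatric safety data as a benefit of the study, and Table 2 plans only 10 infants per gestational-age group, so a single missed infant is visible in a cohort summary.

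**Working it through.** The plan states no figure for this point, so there is none to reproduce. The check is a reading of the sections together, followed by a day count.

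**Step 1: what cancels the call.** Under Section 6.4, any clinical contact before the end of the period does. Under Section 8.3 the complication window begins when the infant leaves the operating room. Section 6.6.2 foresees the child staying in the recovery room or on the surgical ward. Read literally, that stay is already a contact inside the window, and the call would almost never be made. If contact means contact after discharge, one early clinic visit still cancels the call.

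**Step 2: what covers the time after that contact.** Record review continues (synopsis and Sections 6.4, 8.5 and 9). No section requires an inquiry at the end of the window. The guardian self-reporting in Section 8.4 concerns adverse events from specimen collection, which are followed to resolution, 48 hours or discharge, whichever is first. It does not reach the later weeks.

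**Step 3: the share of the window without active inquiry.**

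Inputs:
- Window: Day 2 to Day 31, with surgery on Day 1 (Table 1, Schedule of Study Procedures). Length = 31 − 2 + 1 = 30 days, which agrees with the stated 30-day follow-up.
- Day of last contact, d: an assumption, because the documents give no postoperative visit schedule.

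Formula: share = (31 − d) / 30.

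| Assumed last contact | Days remaining | Share of window |
|---|---|---|
| Day 3 | 28 | 28/30 = 93% |
| Day 7 | 24 | 24/30 = 80% |
| Day 14 | 17 | 17/30 = 57% |
| Day 15 | 16 | 16/30 = 53% |
| Day 16 | 15 | 15/30 = 50% |
| Day 21 | 10 | 10/30 = 33% |
| Day 28 | 3 | 3/30 = 10% |

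The share exceeds half for any last contact up to Day 15. It is small if the infant stays in hospital for long or is seen late.

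**Step 4: what one missed infant would do.** With 10 infants per group (Table 2), an infant whose event is missed lowers that group's proportion by 1/10 = 10 percentage points, and the overall proportion by 1/20 = 5 percentage points. This shows the sensitivity of the summaries. It does not estimate how often a miss would occur.

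**Step 5: whether a call alone would close the gap.** Not for complications. Section 8.3 collects those documented by the anesthesia or surgical teams, so a complication treated elsewhere and reported by a parent has no clear place in the data unless that section changes too.

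**The case against.** The strongest reply is that record review runs through all 30 days and the call is only a backstop to it. That is correct. A reader might infer that most of the window goes unchecked after an early contact. The documents do not support this: Section 6.4 keeps the whole period under review, and Sections 8.5 and 9 say the same. What is missing is active inquiry, not all follow-up.

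Three other inferences also go too far.

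- That infants lost from view are counted as event-free. No section says so. Section 10.2 is silent on incomplete follow-up, which leaves the question open.
- That the record cannot show care at other hospitals. The documents do not say what the reviewed record includes, so this is an assumption.
- That the trigger will almost never fire. This depends on counting the recovery or ward stay as contact. Contact after discharge is arguably the more natural meaning, since the other reading leaves the sentence with little purpose. The text does not settle it.

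It is also fair to say that this is a single-arm PK study of about 20 infants with descriptive safety summaries, no defined 30-day event-rate endpoint and no comparison to bias. This limits the weight of the point but does not remove it. The plan says that it collects these events, and its own trigger can leave them unasked about.

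**Conclusion.** The point holds as a gap in safety ascertainment. Any contact during the period cancels the only inquiry to the parent, and no section requires event status to be confirmed at the end of the window. From the last contact to Day 31, follow-up rests on record review alone: 93%, 80%, 57% or 33% of the window for an assumed last contact on Day 3, 7, 14 or 21.

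Whether events are actually missed depends on the reviewed record not including outside facilities, which the documents leave open. If it does not include them, the omissions run in one direction and the summarized counts can only be too low. The number of missed events cannot be computed from the documents. The primary PK objective, the secondary CYP2A6 objective and the sample size are not affected. This is a modest but worthwhile correction.

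**What to change.** - **Section 6.4:** change the trigger so that every family without a documented clinical contact at or near the end of the window (about Day 30 to 31) is phoned. Define clinical contact for this purpose, and say whether the recovery or ward stay counts.
- **Section 6.4 and the CRF:** record for each infant the date on which event status was last confirmed, so that the Section 10.2 summaries can show how complete follow-up was.
- **Section 8.3:** collect parent-reported complications and readmissions as well as those documented by the anesthesia or surgical teams. Without this change the extra calls would yield information that the complication definition does not take in.

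The cost is at most about 20 short calls by personnel who are already assigned to make such calls, plus some effort to verify what parents report. Treatment, sampling and the PK analysis do not change.

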6.5 End of Therapy OR Early Withdrawal/Discontinuation

As the active participation in the study is only on the day of surgery, it is unlikely that many participants would receive the study drug and not have any samples taken as that time period is usually less than a few hours. Postoperative monitoring will be done remotely, however if any parent/ guardian wishes to be removed from the study and their child's data no longer monitored through the electronic health record, data collection will stop on that patient.

[figure not shown]
6.6 Laboratory Evaluations

6.6.1 Clinical Laboratory Evaluations

For all time points, the following labs may be recorded while the patient is on study if collected per standard of care.

1. Any serum chemistry values obtained during perioperative visits prior to or on the day of surgery and during duration any postoperative stay. These include: WBC, Hg, HCT, Plt, PT, PTT, BUN, serum creatinine, potassium, sodium, AST, ALT, total bilirubin, albumin, prealbumin, ESR, CRP. If multiple values for a laboratory are obtained in the pre- or post-operative period, the values recorded will be the value closest to the day of surgery.

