7.1.2 Dose Frequency

Frequency of metronidazole dosing will be at the discretion of the treating physician.

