10.2 Analysis Plan

Population for Analysis

All enrolled participants with at least 1 evaluable PK sample will be included in the PK analysis and all participants who receive at least 1 dose of study metronidazole will be included in the safety analysis population.

Statistical Methodology

Descriptive statistics, such as number of observations, mean, median, 95% CI, standard deviation, standard error, minimum, and maximum, will be presented by age cohort for continuous variables (such as height, weight, and BMI percentile). Other descriptive statistics, such as counts, proportions, and/or percentages, will be presented by age cohort group to summarize discrete variables (such as race and sex).

Demographics, Baseline Characteristics, and Clinical Course

The number of participants completed and discontinued early from study, and the reasons for discontinuation, will be summarized. Demographic and baseline characteristics will also be summarized. Variables include race, age, sex, ethnicity, and other selected clinical variables will be recorded prior to initiation of study drug. Variables including drug dosing and other selected clinical variables during study drug administration will be recorded.

Safety and Clinical Laboratory Analyses

Laboratory data (serum BUN, serum creatinine, potassium, sodium, AST, ALT, total bilirubin, albumin, prealbumin, ESR, CRP, serum WBC count, Hg, Hct, platelet, PT, PTT) will be tabulated by age cohort. Continuous laboratory measurements will be described using univariable descriptive statistics (mean, median, etc.); observed values and changes from baseline will be summarized. Lab tests reflective of electrolyte abnormalities (e.g., hyponatremia, hypokalemia) will be further summarized in terms of the most extreme values and largest changes from baseline (in the appropriate direction) observed from start of study drug through the end of therapy.

Adverse events and events of special interest will be summarized by age cohort and relationship to drug exposure will be explored. Prior and concomitant medications will be summarized by World Health Organization (WHO) drug class.

PK Analysis

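### Metronidazole-related adverse events are promised but lack a reporting category, and 10.2 does not say which events enter its exposure analysis; the one-value laboratory rule may also fall short of the planned electrolyte extremes

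*Combined protocol and SAP*

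**What the plan says.** **Adverse events.** The scope differs from place to place:

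| Place | Scope |
|---|---|
| 6.4 item 1 | AEs from metronidazole or from study procedures; refers to 8.4 |
| 9 | Harm resulting from the metronidazole infusion is to be collected |
| 15.1 | Investigator responsible for informing the IRB of safety issues with the study or study drug, with SAE reports if required |
| Table 1 footnote f; 6.3 item 8 | Procedure-related AEs |
| 8.4 | AEs and SAEs from specimen collection |
| 8.6 | Reporting of procedure-related AEs, complications and events of special interest |
| 16.1 | Severity and causality assessment of procedure-related AEs and complications |
| 10.2 | AEs (unqualified) and events of special interest, summarized by age cohort and explored against drug exposure; complications not named |

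**Laboratory values.** When a test is repeated in the pre- or post-operative period, 6.6.1 states that "the values recorded will be the value closest to the day of surgery". Under 10.2, electrolyte tests are to be "further summarized in terms of the most extreme values and largest changes from baseline", "observed from start of study drug through the end of therapy". No section says when therapy ends. Section 6.5 carries the term in its heading but gives no time point; it opens "As the active participation in the study is only on the day of surgery". Section 5.3 describes "a 1-day Treatment Period on the day of the operation", and Table 1 marks drug administration for Day 1 only. Section 7.1.2, however, says "Frequency of metronidazole dosing will be at the discretion of the treating physician".

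**The concern.** The AE passages cannot all be followed as written. A reader who builds the AE data set from 8.4 and 8.6 would relate metronidazole exposure to events of special interest and to AEs of blood sampling, such as bruising. A reader who builds it from 6.4 and 9 would also include other drug-related AEs. Section 10.2 does not choose between them. Section 2.3.2 presents safety data on metronidazole as a benefit of the study, so the choice should not be left to whoever assembles the data.

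The laboratory concern is that an extreme-value summary needs every value in its window, whereas 6.6.1 discards repeats. If the discarded values fall inside the window, the worst sodium or potassium value in an infant may never have been recorded.

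**Working it through.** The plan states no figure on this point, so the check traces events and values through the text.

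**Adverse events: where does each kind of event go?**

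1. An AE of specimen collection is covered by 8.4, reported under 8.6 and included in 10.2.
2. A drug-related event that is also an event of special interest (8.1, for example feeding intolerance) is reported under 8.6 and named in 10.2.
3. A drug-related event that is also a complication is reported under 8.6, with causality assessed under 16.1. Footnote g is wide: it takes in any unexpected occurrence needing medical or surgical attention. Section 10.2 does not name complications, so such an event enters the exposure analysis only if the word AE is read to include it.
4. A drug-related AE that is neither is within the commitments of 6.4 item 1 and Section 9. The 6.4 cross-reference leads to 8.4, which covers specimen collection only, and 8.6 lists no category for it. An example is a mild event learned only from the phone call that 6.4 requires when there has been no clinical contact. Sections 8.2 and 8.3 collect complications that the anesthesia or surgical teams have documented, and this event would not be among them.

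The unresolved cases are therefore type 4 (no reporting category, and unclear entry into 10.2) and type 3 (reported, but unclear entry into 10.2).

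**Laboratory: direction of the effect.** Let x₁, …, x_k be an infant's post-dose values of one test in the 10.2 window, and let R be the recorded subset. Then

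min(R) ≥ min(x₁, …, x_k) and max(R) ≤ max(x₁, …, x_k).

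Equality is guaranteed when k = 1 or when all k values are recorded. The baseline is a single fixed value (the most recent pre-operative one, 6.2 item 4), so the largest fall or rise from baseline moves the same way. The recorded result can equal or understate the true extreme and cannot exceed it. Of the 17 tests listed in 6.6.1, 2 are electrolytes (potassium and sodium).

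**Laboratory: which values are recorded?** For Day 1, 6.3 item 3 provides for "Laboratory determinations, if available, no blood draws will be performed just for the purposes of this study" and states no limit on the number of values. Item 6 refers Day 1 results back to 6.6.1.

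| Reading | Values kept in the window | Consequence |
|---|---|---|
| Window is Day 1; all Day 1 values recorded | All | Little or nothing lost |
| Window is Day 1; values after surgery count as post-operative | Those before the post-operative period, plus one | Can understate; a rule that selects by day does not choose among same-day values |
| Window runs past Day 1; all Day 1 values recorded | All post-dose Day 1 values, plus one later value | Can understate if tests are repeated later |

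The second reading is possible because 8.3 dates post-operative complications from leaving the operating room, whereas Table 1 starts the Postoperative Period on Day 2. The third is possible because 7.1.2 leaves dose frequency open and 6.6.1 allows values from any post-operative stay, although Table 1 marks laboratory parameters for Screening and Day 1 only.

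The documents give no number of repeat tests per infant, no duration of therapy and no AE rate, so no amount can be attached to either effect.

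**The case against.** **Laboratory.** The calendar reading is the more natural one. Table 1 and 5.3 both make treatment a single day, 6.3 treats the whole of Day 1 as the operative day, and 6.1 requires adherence to the schedule. Section 8.3 defines when a complication is post-operative and does not define laboratory periods. The opening of 6.6.1 is permissive, so its difference from the laboratory row of Table 1 is weak evidence of conflict. All of this stands, and it is why the point is conditional. A reader might infer that the electrolyte summary is bound to be wrong. The documents do not support that, because on the reading they favor little is lost. What remains is that 10.2 does not state its window.

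**Adverse events.** Footnote g, the causality assessment of complications in 16.1, the events of special interest in 8.1 and the phone call in 6.4 would together capture most drug-related harm of clinical weight. A reader might infer that drug-related harm will not be collected at all; 6.4 and Section 9 say the opposite. A reader might also infer that a dosed infant who is replaced drops out of drug-related AE monitoring, because 5.3.1 does not list such AEs. But 5.3.1 refers to the protocol generally, so 6.4 can still apply, and silence is not exclusion. Section 15.1 is a duty to the IRB and does not define the 10.2 data set. The CRF is not among the documents and may already hold a suitable field. These arguments narrow the gap, but they do not repair the 6.4 cross-reference, add a category to 8.6 or say which AEs 10.2 means.

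Safety is not among the objectives or outcome measures in Section 3, and dosing follows standard care. That limits the importance of the point but does not remove the inconsistency.

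**Conclusion.** The AE point holds without assumptions about data. Two sections promise metronidazole-related AEs, the sections that define and report AEs have no category for those that are neither complications nor events of special interest, and 10.2 analyzes AEs against exposure without saying which. Two careful analysts could produce different tables from the same plan.

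The laboratory point holds conditionally. It has no practical effect if the window is Day 1 and every Day 1 value is recorded. It matters if the window runs further, or if values after surgery on Day 1 count as post-operative, and then only for an infant with repeated sodium or potassium values. The direction is fixed (equal to or less extreme than the truth), but the amount cannot be computed.

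Both points affect descriptive safety output only. The primary PK analysis is untouched.

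**What to change.** **Adverse events.** Reconcile Table 1 footnote f and Sections 6.3, 6.4, 8.4, 8.6, 9, 15.1 and 16.1 so that metronidazole-related AEs have a collection and reporting category. Correct the 6.4 cross-reference to 8.4. In 10.2, name the events that enter the exposure analysis and say whether complications are among them.

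**Laboratory.** In 10.2, define the window for the extreme-value summary, as an analysis definition only. In 6.6.1, provide for recording all dated and timed post-dose sodium and potassium values that the medical record already holds within that window, and keep the closest-value rule for baseline. State whether values after surgery on Day 1 count as post-operative, and align the laboratory row of Table 1. Alternatively, delete the extreme-value summary.

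**Cost.** Wording changes, some extra abstraction from existing records (the number of values is unknown) and possibly one added CRF field. No extra blood draws or visits are needed.
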